## STATISTICAL PLAN:

Statistical Analysis: Data will be analyzed using SAS (SAS 9.4, Cary, N.C.). Baseline statistics per treatment group will be obtained. Bivariate analysis of covariates (age, sex, race/ethnicity, asthma severity, phenotype (i.e. atopic), socioeconomic status (SES), exposure to primary or secondary tobacco smoke, FeNO, use of controller medication, etc) between groups will be conducted using student t-test or Wilcoxon rank sum and Fisher's exact or Chi-square (where appropriate and based on distribution). Variables with significant differences between groups ( $P<0.05$ ) will be considered for inclusion in multivariate model selection. The effects of physical activity on the outcomes will be compared between groups. Baseline knowledge and usage of AQI will be assessed. Adherence to AQI will also be assessed and compared between groups, with potential stratification by AQI usage. Additionally, differences in weight and BMI will be assessed to evaluate if adherence to AQI promotes sedentarism and leads to increased weight gain. We will evaluate our outcomes (Aims 2 and 3) in three ways. First, we will evaluate the average difference (overall mean) between groups for our primary outcomes using T test or chi-square (where appropriate). Additionally, we will test the average mean difference between each treatment group by multivariate regression (linear for PAQLQ and ACT or CACT, and/or Poisson or logistic regression for mean asthma exacerbations depending on distribution) to allow for covariate adjustment. Second, we will use paired t-tests (or matched Wilcoxon signed-rank) to evaluate the within group effects (6 month mean – baseline) for each primary outcome. Third, to assess the effects over time in our intervention study (correlated repeat measures data), we anticipate analyzing our primary outcomes by generalized linear mixed models (GLMM). For these models, we will first evaluate the distribution of our primary outcome and determine the most appropriate link (e.g. for severe asthma exacerbations: logistic link if there are overall a high proportion of participants with none, or Poisson link if more consistent with count data). A stepwise approach will be used to build all multivariable models. All final models will include age, sex, race/ethnicity, SES, and tobacco smoke exposure. Additionally, the above outcomes will be stratified by age group (8-12y, 13-17y) to determine if the effects are greater in older children for whom the AQI recommendations may be better self-incorporated into outdoor physical activities, vs the younger group who will likely be more reliant on parental checking and activity modification.

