
Power calculations: Power calculations were conducted using G\*Power 354 and SAS (SAS 9.4, Cary, N.C.) using proc glmpower. For mean difference between treatment groups (routine vs. intervention) with sample size of 20 participants per group, two-tailed test, alpha 0.05, we will have  $\geq 90\%$  power to detect a mean difference of 1.05 between groups for mean asthma exacerbations, ACT and C-CACT, and PAQLQ. Our study will provide  $\geq 80\%$  power to detect a mean difference of 0.91. As the clinical difference for ACT is 2-3 points, we anticipate adequate power to detect a clinical difference. The estimated clinically meaningful difference in PAQLQ is 0.5, and our study may be underpowered to detect this small of difference with this analysis. For comparison within each treatment group, comparing the matched difference (end of study- baseline), using the same assumptions above, we will have  $\geq 90\%$  power to detect a mean difference of 0.76, and  $\geq 80\%$  power to detect a mean difference of 0.66. Therefore, we expect better ability to detect changes in PAQLQ within the groups than between them. For repeat measures, we estimated our power using proc glmpower using F test based on Hotelling-Lawley trace. We estimated a study allocation of 1:1, alpha 0.05, repeated measures at 1, 2, 3, 4, 5 months, lear correlation structure with base correlation 0.85 & decay rate of 1, with an estimated mean difference of 2, standard deviation of 2, which provides a  $\geq 90\%$  power for a treatment group size of 12 for overall mean and n=26 for time\*treatment.

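### The between-arm analyses of ACT/C-ACT and PAQLQ do not fix the baseline score as a covariate, although it is collected at Visit 1

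*Combined protocol and SAP*

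**What the plan says.** Tables 1 and 2 schedule ACT or C-ACT and PAQLQ at Visit 1. Section 2.1 (Aim 3) places the quality-of-life assessments before randomization and at 6 months.

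The Statistical Plan evaluates Aims 2 and 3 in three ways:

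- **Between arms.** A t-test, then linear regression for PAQLQ and ACT/C-ACT with covariate adjustment.
- **Within each arm.** "we will use paired t-tests (or matched Wilcoxon signed-rank) to evaluate the within group effects".
- **Over time.** A generalized linear mixed model (GLMM) for the primary outcomes.

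On covariates it says "All final models will include age, sex, race/ethnicity, SES, and tobacco smoke exposure". A further list of baseline variables ends open and does not name the baseline outcome score. Variables on it that differ between arms at P<0.05 "will be considered for inclusion in multivariate model selection". It adds: "A stepwise approach will be used to build all multivariable models".

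The power paragraph concedes, for a PAQLQ difference of 0.5, that "our study may be underpowered to detect this small of difference with this analysis", and expects within-arm comparisons to detect PAQLQ changes better. For ACT it says: "As the clinical difference for ACT is 2-3 points, we anticipate adequate power to detect a clinical difference".

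**The concern.** The hypothesis in section 2.1 is about adding the AQI to the action plan, so the between-arm contrast answers it. For PAQLQ the plan itself regards that contrast as possibly underpowered. The baseline score is often the strongest available predictor of the follow-up score, and it is already being collected. Yet the first-listed test ignores it, and the regression leaves its inclusion to the data.

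An imbalance screen is a poor way to choose it. Under randomization the screen flags any given variable about 5% of the time, whatever its prognostic value. At stake is between-arm precision in a trial of 40 children. The plan's response to low PAQLQ power is to point to the within-arm tests, but those answer a different question: both arms receive an action plan, the same AQI education and monthly calls.

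**Working it through.** **Inputs.** From the power paragraph: 20 per arm, two-sided alpha 0.05, PAQLQ difference 0.5, ACT difference 2 to 3 points. No PAQLQ SD is given, so 0.8, 1 and 1.2 are assumed. No baseline-to-follow-up correlation is given, so r = 0.3, 0.5, 0.7 and 0.85 are assumed. The top value equals the base correlation in the plan's repeated-measures calculation; applying it from baseline to month 6 is an assumption.

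**1. The plan's own figures.** Noncentral t, 38 df, noncentrality = difference / (SD × √(2/20)), with √(2/20) = 0.3162. At SD 1:

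- 0.91 gives 0.91/0.3162 = 2.88 and power 80.1%.
- 1.05 gives 1.05/0.3162 = 3.32 and power 89.9%.

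The stated 80% and 90% reproduce, so the detectable differences are in effect SD units.

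**2. PAQLQ difference of 0.5.** The effective SD is:

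- unadjusted: SD (38 df)
- ANCOVA: SD × √(1 − r²) (37 df)
- change score: SD × √(2(1 − r)) (38 df)

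Example at SD 1, r = 0.5: the ANCOVA SD is 0.866, noncentrality 0.5/(0.866 × 0.3162) = 1.83, power 42.8%. The change-score SD is 1, noncentrality 1.58, power 33.8%.

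| SD | Contrast | r 0.3 | r 0.5 | r 0.7 | r 0.85 |
|---|---|---|---|---|---|
| 1 | Unadjusted | 33.8% | 33.8% | 33.8% | 33.8% |
| 1 | Change score | 25.6% | 33.8% | 51.2% | 80.3% |
| 1 | ANCOVA | 36.5% | 42.8% | 57.8% | 83.2% |
| 1 | Gain over the better of the other two (points) | 2.7 | 9.0 | 6.6 | 2.9 |
| 0.8 | Unadjusted | 48.7% | 48.7% | 48.7% | 48.7% |
| 0.8 | Change score | 37.0% | 48.7% | 70.1% | 94.0% |
| 0.8 | ANCOVA | 52.3% | 60.4% | 76.9% | 95.5% |
| 1.2 | Unadjusted | 25.0% | 25.0% | 25.0% | 25.0% |
| 1.2 | Change score | 19.2% | 25.0% | 38.2% | 65.0% |
| 1.2 | ANCOVA | 27.0% | 31.7% | 43.5% | 68.3% |

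The largest gain over the better alternative anywhere in the table is 60.4 − 48.7 = 11.7 points (SD 0.8, r = 0.5).

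**3. What the data-driven routes would deliver.** Simulation at SD 1, 20 per arm, difference 0.5, r in the same order:

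- Imbalance screen as the only route: baseline enters about 5% of the time and power stays at 34% to 35% for every r. Type I error is 5.0%, 4.3%, 3.7% and 2.7%, so there is no inflation.
- Stepwise entry on association with the outcome: baseline enters 47%, 91%, over 99% and 100% of the time. Power is about 36%, 42%, 56% and 83%.
- Baseline fixed in advance, in simulation: 36%, 42%, 56% and 82%. This is slightly below the closed form, which ignores chance baseline imbalance.

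**4. ACT difference of 2 points.** The only SD in the plan is 2, given for the repeated-measures calculation without naming an outcome. At that SD, unadjusted power is 86.9% and ANCOVA gives 89.8%, 94.5%, 99.1% and over 99%. At an assumed SD of 3, unadjusted power is 53.8% and ANCOVA gives 57.6%, 65.9%, 82.0% and 97.4%.

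**5. Cost in degrees of freedom.** With 30 error df instead of 37, ANCOVA power at SD 1 is 36.1%, 42.4%, 57.3% and 82.7%, less than 1 point lower.

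**6. Role of baseline in the GLMM.** The plan does not state it. The power inputs place the repeated measures at months 1 to 5, with no month 0, and size the model as "treatment group size of 12 for overall mean and n=26 for time" by treatment. For ACT/C-ACT this suggests that baseline is not a response. PAQLQ has only two planned assessments, so a repeated-measures model for it is possible only if baseline is a response.

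**The case against.** Three objections have force.

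- **Baseline is not shut out.** A reader might infer that its information is lost altogether. The text does not support that: the covariate list is open-ended, flagged variables are only considered, and stepwise building is a separate statement. If baseline is a stepwise candidate, the power is nearly that of fixed adjustment. What stands is that the route is unspecified, and the outcome ranges from no gain to almost the full gain.
- **34% against 83% is too generous a comparison.** If the PAQLQ mixed model takes baseline as a response, it resembles a change-score contrast, which already reaches 80% at r = 0.85. This stands, although the plan does not say which contrast it would rely on.
- **The within-arm tests are legitimate.** Aim 3 asks for within-group and between-group evaluation, and the between-arm comparison is listed first. A reader might infer that a significant change in the intervention arm alone would count as efficacy. The plan states no such rule, so no error rate should be attached to it.

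This is also a 40-child proof-of-concept pilot that discloses its limited PAQLQ power.

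**Conclusion.** The concern holds as a gap in prespecification. The between-arm analyses of ACT/C-ACT and PAQLQ do not fix the baseline score, and the routes left open depend on the data. At an assumed PAQLQ SD of 1, fixed adjustment raises power for a 0.5 difference from 34% to between 37% and 83% over r = 0.3 to 0.85. The gain is about 3 to 9 points over the better of the unadjusted and change-score contrasts, and close to nothing over stepwise entry on association with the outcome. For ACT at an SD of 2 little is at stake.

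All of this rests on an SD and a correlation that the documents do not supply, and the gain shrinks if the forced covariates already explain part of the outcome. It would be wrong to read the gap as inflated type I error or average bias. The change should be made because it is nearly free, not because the plan is invalid without it.

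**What to change.** In the Statistical Plan:

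- Make the primary between-arm analysis of PAQLQ an ANCOVA, and that of ACT/C-ACT an ANCOVA or a mixed model over Visits 2 to 7. Fix the baseline score, arm and the five listed covariates in advance.
- State that covariates in these models are not chosen by the imbalance screen or by stepwise selection.
- Confirm the role of baseline in the GLMM: covariate or response.
- State that the between-arm contrast is the test of adding the AQI. Keep the paired tests that Aim 3 calls for, labelled supportive, and reword the power sentence that favours them for PAQLQ.

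The cost is plan wording and one degree of freedom for the baseline score. No new data or participants are needed.

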## 2. STUDY DESIGN:

Longitudinal (6 month) intervention trial, simple randomized 1:1 with stratification based on age (8-12 years, 13-17 years), non-blinded, to determine if adding the AQI to asthma action plans (AAP) reduces asthma exacerbations, and improves asthma control and quality of life (Figure 3).

Both groups will receive basic education about the AQI including what the AQI is, where to find it, how to use it, and behavioral recommendations by category. In our practice, discussion of the AQI varies by practitioner and patients. While true routine care is likely absence of discussion of the AQI, this was determined to be inappropriate for this study. First, consenting children to the study would result in some discussion of the AQI and therefore bias any true “routine care”. Second, we did not wish to withhold potentially vital asthma self-management to participants. Therefore, all children in the study will receive AQI

[figure not shown]
education. The routine group will receive written AAP only, and the intervention group will receive AAP + AQI written plan. Additionally, the intervention group will be required to download the app onto their or their parent's smartphone (available both for iPhone or android phones) **or** demonstrate the ability to navigate to the airnow.gov website to obtain the AQI at their location. Participants will be followed at monthly intervals for 6 months.

The goal of the AQI is to familiarize persons to their own sensitivities to air pollution and encourage self-modification as needed for personal symptom control. Additionally, there is a goal to prevent discouraging physical activity as most US persons do not meet current daily recommendations.

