### 2.1 Hypothesis and Specific Aims

We hypothesize that the addition of the AQI to AAP will (A) reduce asthma exacerbations, and (B) improve symptom control & quality of life in children with asthma. To test these hypotheses, in this study we will pursue the following specific aims:

- Aim 1: To recruit a pilot cohort of 40 children with asthma. For proof of concept, we will recruit 40 children with asthma from Children's Hospital of Pittsburgh, the only children's hospital serving southwest Pennsylvania (metropolitan area >2.6 million people). Baseline knowledge about the AQI including familiarity, usage, and prior healthcare provider discussion will be assessed.

- Aim 2: To evaluate if the addition of the AQI to AAP reduces asthma exacerbations in a pilot study of children. Participating children (Aim 1) will be randomized to one of two groups. All participants/caregivers will receive an AAP and verbal AQI education. The intervention group will additionally demonstrate the ability to check the AQI, and AQI recommendations will be incorporated onto their written AAP. Children will be followed monthly for 6 months to evaluate adherence to AQI recommendations and assess the frequency of asthma exacerbations, defined per ATS guidelines. Other known factors contributing to asthma exacerbations, such as asthma severity, viral illnesses, allergic triggers will also be monitored.
- Aim 3: To examine whether the addition of the AQI to AAP improves asthma symptom control and quality of life in a pilot study of children. Asthma symptom control will be measured in participating children monthly, and quality of life will be assessed before randomization and at 6 months. Symptom control and quality of life will be evaluated within (before/after intervention) and between groups.

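### With 40 children, five forced covariates plus stepwise selection make an ordinary logistic model of exacerbations unstable, and a real treatment effect is estimated too far from the null

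*Combined protocol and SAP*

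**What the plan says.** All of the following is in the STATISTICAL PLAN section unless noted.

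- Forced terms: "All final models will include age, sex, race/ethnicity, SES, and tobacco smoke exposure".
- Model building: "A stepwise approach will be used to build all multivariable models". No entry or stay threshold and no limit on terms is given. Covariates that differ between arms at P<0.05 are also considered, from an open-ended list that includes severity, phenotype, FeNO and controller use.
- Exacerbations may be analysed by Poisson or logistic regression, depending on their distribution. For the mixed models, the example given for severe exacerbations is a "logistic link if there are overall a high proportion of participants with none".
- The outcomes are also to be stratified by the two age groups.
- An unadjusted t test or chi-square comparison is listed first.
- The sample is 40 children (section 2.1, Aim 1), and the power paragraph works "with sample size of 20 participants per group, two-tailed test, alpha 0.05".

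The plan gives no expected exacerbation rate, age-group size, dropout figure or coding for race/ethnicity and SES. It names no penalised or exact method and has no rule for a model without a finite estimate.

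**The concern.** The information in a logistic model is set by the number of children with an event, not by the number enrolled. The plan's own example turns to logistic when most children have none, so events may be scarce exactly where the covariate list stays fixed and stepwise terms can be added. Ordinary maximum likelihood then has two known failures. Estimates can be infinite because some combination of covariates separates the outcomes, and finite estimates lie too far from zero.

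Aim 2 asks whether exacerbations fall. If they do, an exaggerated or inestimable odds ratio would mislead a reader of the pilot, including anyone who uses it to size a later trial.

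**Working it through.** **1. The plan's own figures.** The power paragraph claims at least 90% "power to detect a mean difference of 1.05 between groups for mean asthma exacerbations" and at least 80% "power to detect a mean difference of 0.91". No SD is stated; SD = 1 is implied. For a two-sample t test the noncentrality is d × √(n/2), with n = 20 and 38 df: 1.05 × √10 = 3.32 gives 89.9%, and 0.91 × √10 = 2.88 gives 80.1%. The figures reproduce to rounding, but they concern means. No power figure covers a logistic model.

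**2. Events per parameter.** Arm plus five covariates at one term each is 6 parameters, the minimum.

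- 40 children: 40 × 0.20 / 6 = 1.3; 40 × 0.30 / 6 = 2.0.
- 20 children (one age group, even split assumed): 20 × 0.20 / 6 = 0.7; 20 × 0.30 / 6 = 1.0.

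More levels for race/ethnicity or SES, and any stepwise term, lower these.

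**3. Simulation.** Model: logit P(event) = a + covariate effects + β × arm, with one record per child, 20 per arm, and a set to give the chosen control risk. The assumptions are control risks of 20, 30 and 50%; β = ln 0.40 = -0.92 or 0; modest covariate effects; and race/ethnicity and SES with one term each or with three levels.

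Results at n = 40, 30% control risk and true log OR -0.92 (ranges span several sets of runs with different codings and covariate effects; maximum-likelihood rows use fits with a finite estimate):

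| Model | Median log OR | SD |
|---|---|---|
| Five covariates forced, maximum likelihood | about -1.13 to -1.2 | 1.2 to 1.6 |
| Small or unadjusted | -0.89 to -0.98 | 0.84 to 0.92 |
| Five covariates forced, Firth | -0.83 to -0.92 | 0.85 to 0.98 |

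The forced model's excess is (1.13 − 0.92)/0.92 = 23% to (1.2 − 0.92)/0.92 = 30% on the log scale, so an odds ratio of 0.40 is typically reported as 0.30 to 0.32. At n = 400 the same forced model has a median of -0.92, so this is small-sample bias.

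One set of runs with one-term covariates shows how the result moves with control risk (median, SD in brackets). Stepwise here means forward entry at p<0.15 from four noise candidates, an assumed rule.

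| Control risk | Forced | Forced + stepwise | Unadjusted |
|---|---|---|---|
| 20% | -0.93 (2.07) | -1.08 (2.44) | -0.75 (0.84) |
| 30% | -1.15 (1.48) | -1.31 (1.91) | -0.98 (0.84) |
| 50% | -1.18 (1.05) | -1.28 (1.38) | -0.90 (0.75) |

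The 20% row is not reassuring. It leaves out the 33% of forced fits with no finite solution, and the SD of the rest is about 2.5 times that of the unadjusted model (2.07/0.84).

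**4. Separation of the treatment term, n = 40.** With OR 0.4 it has no finite estimate in about 4–8% of trials at 30% control risk and 16–22% at 20%; under no effect, in about 0–6%. Much of the OR 0.4 figure comes from an arm with no events, which no covariate choice prevents. At 20% control risk the intervention odds are 0.25 × 0.4 = 0.10, a risk of 0.091, and 0.909^20 = 0.15. At 30%, the odds are 0.429 × 0.4 = 0.171, a risk of 0.146, and 0.854^20 = 0.04.

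**5. Within age groups of about 20.** If the adjusted logistic model is fitted there, the treatment term separates in roughly 7–50% of trials under no effect, depending on event rate and coding. In the one-term runs an unadjusted fit failed in 4% and 1% at 30% and 50% control risk.

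**6. No true effect, n = 40, 30% risk.** The median stays near 0, but the SD rises from 0.70 (unadjusted) to 1.00 (forced) and 1.36 (stepwise). Across the settings run, Wald rejection was 4–7% at n = 40 and 0–2% at n = 20.

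**The case against.** Several stronger conclusions are tempting, and the documents do not support them.

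- *Stepwise selection inflates the type I error.* This is not shown for the logistic models (step 6). In a linear model at n = 40, unscreened entry of six noise covariates at an assumed p<0.15 gives 7.0–7.9%, against 4.5–5.3% with forced terms only. If candidates must first differ between arms at P<0.05, which is the more natural reading of the plan, the figure is 5.4%.
- *Up to half of trials lose the result.* With three-level race/ethnicity and SES and no effect, some coefficient is infinite in about 11–50% of fits at n = 40. That is usually a sparse covariate level; the treatment term is affected far less often (step 4).
- *The plan commits exacerbations to a logistic model, and to a full refit by age group.* It does neither. Poisson remains open, and the sentence on a high proportion with none is an example for severe exacerbations in the mixed model. Moderate events also count under section 2.2, so the proportion with any exacerbation may be higher. The age sentence does not say that the adjusted model is refitted, and no age-group sizes are fixed.
- *The five covariates should be dropped.* They are prespecified, and Firth removes most of the bias with them kept. Demoting them is a preference.

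It is also fair that this is a pilot and that the unadjusted comparison comes first and is unaffected. That lowers the stakes, but the adjusted models are still planned and would be reported.

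**Conclusion.** The concern holds for ordinary logistic fits of exacerbations. At n = 40 and 30% control risk, a true log OR of -0.92 is estimated with a median about 23–30% too large and clearly more spread than in a small model. Stepwise selection under the assumed rule adds to both. The direction is away from the null when an effect exists; with no effect only the spread grows. Fits within age groups of about 20 would often give no usable treatment estimate.

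The size depends on assumed event rates, covariate coding, covariate effects, stepwise threshold and an even age split. The Poisson models and the logistic mixed model on monthly data were not simulated, so nothing is claimed about their size of error. This should be corrected before analysis, but it does not undermine the trial's unadjusted comparisons.

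**What to change.** Three changes to the wording of the statistical plan:

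1. Replace the stepwise sentence with a covariate list fixed in advance, including the age stratum used in randomisation and, where collected, the baseline value of the outcome. The five named covariates may stay. State how race/ethnicity and SES will be coded.
2. Specify Firth-penalised likelihood for any logistic fit, and say what will be done if the logistic mixed model is used.
3. Within age groups, report only the treatment effect, unadjusted or from a minimal penalised model.

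No data collection changes. The price is slight shrinkage of the estimate toward the null and the loss of data-driven adjustment for chance imbalance. Baseline differences would still be visible in the planned comparison of covariates by arm.

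### Whether the effect is greater in older children is to be judged from age-stratified analyses, with no arm-by-age interaction or other comparison between strata named

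*Combined protocol and SAP*

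**What the plan says.** The closing sentence of the statistical analysis paragraph (STATISTICAL PLAN) states that "the above outcomes will be stratified by age group (8-12y, 13-17y) to determine if the effects are greater in older children". The reason given is that adolescents may act on the AQI advice themselves, while younger children depend more on a parent.

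The same age groups are used in the randomisation (section 2, STUDY DESIGN): "simple randomized 1:1 with stratification based on age (8-12 years, 13-17 years". No target number is set for either stratum.

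In the models, age is an adjustment variable: "All final models will include age, sex, race/ethnicity, SES, and tobacco smoke exposure". Other terms enter by selection: "A stepwise approach will be used to build all multivariable models". No arm-by-age term is listed. The only interaction mentioned anywhere is time by treatment, in the power paragraph.

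On size, section 2.1 says "we will recruit 40 children with asthma from Children's Hospital of Pittsburgh", and the power paragraph assumes a "sample size of 20 participants per group, two-tailed test, alpha 0.05". No power or precision is given for the age question.

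**The concern.** The plan wants to know whether one effect is larger than another. Repeating the analyses in each stratum gives two estimates and two p-values, but no estimate of the difference between them and no measure of its uncertainty. With strata this small, one p-value can easily fall below 0.05 and the other above it when the true effects are the same. Two estimates can also lie well apart by chance.

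At stake is a secondary conclusion, not the main comparison of arms. A pilot report that the AQI plan helps adolescents but not younger children could still shape the age range or the intervention of a later trial.

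**Working it through.** **Inputs.** 40 children, 20 per arm, two-sided alpha 0.05 (section 2.1 and the power paragraph). Two age strata (section 2). Planning effects: 90% "power to detect a mean difference of 1.05 between groups for mean asthma exacerbations, ACT and C-CACT, and PAQLQ", and 80% "power to detect a mean difference of 0.91". Assumptions of this check: a continuous outcome, a two-sample t-test, no dropout, and an even age split, so 40 / 2 arms / 2 strata = 10 per arm per stratum. Uneven splits are shown below. The 0.5 SD effect is an illustrative smaller value, not a figure from the plan.

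**Step 1: reproduce the plan's power.** With SD = 1, noncentrality = d x sqrt(n/2), df = 2n - 2. For n = 20:
- d = 1.05: noncentrality 3.32, power 0.899.
- d = 0.91: noncentrality 2.88, power 0.801.

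The stated 90% and 80% are recovered, so 1.05 and 0.91 behave as standardised differences and are used as such here.

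**Step 2: power within one stratum, and the chance that exactly one stratum is significant.** Same test with n = 10 per arm (df = 18). If both strata have the same true effect and the same power p, P(exactly one significant) = 2p(1 - p).

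| True effect in both strata | Power per stratum | Exactly one significant | Older stratum only |
|---|---|---|---|
| 0 | 0.050 | 2 x 0.050 x 0.950 = 9.5% | 4.8% |
| 0.5 SD | 0.185 | 2 x 0.185 x 0.815 = 30% | 15% |
| 0.91 SD | 0.486 | 2 x 0.486 x 0.514 = 50% | 25% |
| 1.05 SD | 0.603 | 2 x 0.603 x 0.397 = 48% | 24% |
| 1.3 SD | 0.785 | 2 x 0.785 x 0.215 = 34% | 17% |

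**Step 3: uneven age splits.** P(exactly one) = p1(1 - p2) + p2(1 - p1).
- 12/8 per arm: at 0.91 SD, 0.568 x 0.604 + 0.396 x 0.432 = 51%; at 1.05 SD, 0.691 x 0.502 + 0.498 x 0.309 = 50%.
- 15/5 per arm: at 0.91 SD, 0.672 x 0.754 + 0.246 x 0.328 = 59%; at 1.05 SD, 0.793 x 0.690 + 0.310 x 0.207 = 61%.

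The total is therefore 50-61% over these splits, but it no longer divides equally. Over the same cases the older stratum alone is significant in 6-17% of trials if it is the smaller one, and in 34-55% if it is the larger.

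**Step 4: what an interaction test can do.** The interaction is the difference between the two stratum-specific arm differences. Its SE = SD x sqrt(2/10 + 2/10) = 0.632 SD, with 36 df.
- 95% CI half-width: 2.028 x 0.632 = 1.28 SD.
- Power: 29% for a true interaction of 0.91 SD and 37% for 1.05 SD.
- Detectable interaction: 1.82 SD at 80% power and 2.11 SD at 90%.
- With no true interaction, the two stratum estimates still differ by 0.50 SD on average (0.632 x 0.798), and by more than 0.91 SD in about 15% of trials.

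About 78 per arm would be needed for 80% power at an interaction of 0.91 SD.

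**Step 5: asthma control.** Section 2.2 uses C-ACT at ages 8-11 and ACT from 12. The older stratum is measured entirely by ACT; the younger one by C-ACT, apart from the 12-year-olds. A raw-score age contrast on this outcome mixes age with instrument.

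**The case against.** Several counter-arguments have force.

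- **No decision rule is stated.** A reader might infer that the investigators will claim effect modification whenever one stratum is significant and the other is not. The documents do not say that. Comparing the two estimates informally fits the text equally well. What can be shown is that the method of comparison is missing. The percentages say how misleading one natural way of filling the gap would be.
- **The figures depend on the effect assumed.** With an even split, 2p(1 - p) cannot exceed 50%, and the plan's two planning effects lie at or near that ceiling. At smaller or larger effects the figure is lower, and the plan's question is directional, so with an even split only half of the cases favour older children. A reader might infer that a false age conclusion is likely; the range does not support that in general.
- **The calculation covers one type of analysis.** It does not carry over directly to the Poisson or logistic models for exacerbations, the paired tests or the mixed models. The 5% false-positive rate of an interaction test likewise applies to one such test on one continuous outcome.
- **The question is peripheral.** It is not among the hypotheses or aims, the study is described as a pilot, and no power is claimed for it. That limits the consequence. It does not supply a method, and the plan does not label the analysis exploratory.
- **An interaction test has little power here.** True. It gives a valid comparison, and its interval shows how little can be learned, but it will rarely settle the question.

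**Conclusion.** The point stands as a gap in method: the plan poses a comparative question about age and names no comparison that answers it. Under the assumptions above, equal true effects produce significance in exactly one stratum in about 10% of trials with no effect, 30% at 0.5 SD and 48-50% at the plan's own effects, with half favouring the older group when the split is even. Uneven splits from 12/8 to 15/5 give 50-61% at the plan's effects.

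The documents do not establish that chance differences will be reported as effect modification, and the main comparison of arms is unaffected. The plan should be changed because the correction is cheap and the stated purpose currently has no valid method behind it.

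**What to change.** For each outcome, add arm x age stratum (with the age-stratum main effect) to the model already planned, using whichever link is chosen: identity, log or logit. Keep the term in whatever the stepwise selection does. Then:

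- report the interaction estimate with its 95% CI, and take stratum-specific effects from that model only;
- label the analysis exploratory, and say that 40 children can give only an imprecise answer;
- state that one stratum being significant and the other not will not be taken as effect modification, and that a non-significant interaction will not be taken as equal effects;
- for asthma control, put ACT and C-ACT on a common scale, for example by standardising within instrument, or state that the age contrast is partly confounded with instrument.

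The cost is a short paragraph in the statistical plan and a little programming, with no new data, visits or participants. The drawback is the wide interval. With sparse exacerbation data and the five required covariates, the interaction may be less precise still than the continuous-outcome figures suggest.
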